3.1 Inclusion Criteria

3.11 Age ≥ 18 years.

3.12 The following laboratory values obtained ≤ 7 days prior to registration.

- Absolute neutrophil count (ANC) $\geq 1700/\text{mm}^3$
- Platelet count $\geq 100,000/\text{mm}^3$
- Hemoglobin ≥ 8.0 g/dL
- SGOT (AST) ≤ 3 x upper limit of normal (ULN)
- Creatinine clearance ≥ 30 mL/min (as determined by Cockcroft-Gault equation*)

*Cockcroft-Gault Equations:

$$\text{Creatinine clearance for males} = \frac{(140 - \text{age})(\text{actual body weight in kg})}{(72)(\text{serum creatinine in mg/dL})}$$

$$\text{Creatinine clearance for females} = \frac{(140 - \text{age})(\text{actual body weight in kg})(0.85)}{(72)(\text{serum creatinine in mg/dL})}$$

Example: A woman aged 75, weight 50 kg and creatinine of 1.35 mg/dL has a calculated clearance of 28.

3.13 Diagnosis of multiple myeloma according to International Myeloma Working Group criteria and one of the following:

- SMM
- IMM
- newly diagnosed MM

Note: Patients with lytic disease and anemia are eligible

3.14 High risk disease defined by all of the following:

- $\geq 10\%$ bone marrow plasma cells
AND
- Abnormal serum free light chain (FLC) ratio (< 0.26 or > 1.65) by serum FLC assay
AND
- Monotypic Plasma Cell S-phase $\geq 0.3\%$

3.15 Measureable level of M-protein > 1 g/dL on serum protein electrophoresis or > 200 mg of M-protein on a 24 hour urine protein electrophoresis.

3.16 Negative tuberculosis (TB) testing (Quantiferon – TB blood test or skin test) ≤ 7 days prior to registration.

3.17 ECOG performance status (PS) 0, 1 or 2 ([Appendix I](#)).

- 3.18 Provide signed informed consent.
- 3.19a Negative (serum or urine) pregnancy test done ≤ 7 days prior to registration, for women of childbearing potential only.
NOTE: A second pregnancy test must be performed within 24 hours prior to the start of lenalidomide. The subject may not receive lenalidomide until the study doctor has verified that the results of these pregnancy tests are negative.
- 3.19b Willing to return to enrolling institution for follow-up (during the Active Monitoring Phase of the study).
- 3.19c Willing and able to comply with the requirements of the Revlimid REMS™ program.
- 3.19d Females of childbearing potential must be willing to adhere to the scheduled pregnancy testing as required by the Revlimid REMS™ program.
- 3.2 Exclusion Criteria
- 3.21 Prior treatment with any other agent that may affect M-protein ≤ 30 days prior to registration.

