10.3 Assessment of Attribution

When assessing whether an adverse event is related to a medical treatment or procedure, the following attribution categories are utilized:

Definite - The adverse event *is clearly related* to the agent(s).

Probable - The adverse event *is likely related* to the agent(s).

Possible - The adverse event *may be related* to the agent(s).

Unlikely - The adverse event *is doubtfully related* to the agent(s).

Unrelated - The adverse event *is clearly NOT related* to the agent(s).

Events determined to be possibly, probably or definitely attributed to a medical treatment suggest there is evidence to indicate a causal relationship between the drug and the adverse event.

10.4 Expedited Reporting Requirements for Studies using Commercial Agent(s) ONLY:

Expedited Reporting Requirements for Adverse Events that Occur in a Non-IND/IDE trial within 30 Days of the Last Administration of a Commercial Imaging Agent^{1,2}

FDA REPORTING REQUIREMENTS FOR SERIOUS ADVERSE EVENTS (21 CFR Part 312) NOTE: Investigators MUST immediately report to the sponsor ANY Serious Adverse Events, whether or not they are considered related to the investigational agent(s)/intervention (21 CFR 312.64) An adverse event is considered serious if it results in ANY of the following outcomes:
 
 1) Death 2) A life-threatening adverse event 3) An adverse event that results in inpatient hospitalization or prolongation of existing hospitalization for ≥ 24 hours 4) A persistent or significant incapacity or substantial disruption of the ability to conduct normal life functions 5) A congenital anomaly/birth defect. 6) Important Medical Events (IME) that may not result in death, be life threatening, or require hospitalization may be considered serious when, based upon medical judgment, they may jeopardize the patient or subject and may require medical or surgical intervention to prevent one of the outcomes listed in this definition. (FDA, 21 CFR 312.32; ICH E2A and ICH E6). 				

ALL SERIOUS adverse events that meet the above criteria MUST be immediately reported to the sponsor within the timeframes detailed in the table below.
				
Hospitalization	Grade 1 Timeframes	Grade 2 Timeframes	Grade 3 Timeframes	Grade 4 & 5 Timeframes
Resulting in Hospitalization ≥24 hrs	7 Calendar Days			24-Hour 3 Calendar Days
Not resulting in Hospitalization ≥ 24 hrs	Not required		7 Calendar Days	

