10.6 Required Routine Reporting

Adverse events to be graded at each evaluation and pretreatment symptoms/conditions to be evaluated at baseline per the CTCAE v4.0 grading unless otherwise stated in the table below:

SYSTEM ORGAN CLASS	Adverse event/Symptoms	Baseline	Each evaluation
Investigations	Creatinine increased	X	X
	Neutrophil count decreased	X	X
	Platelet count decreased	X	X
	Lymphocyte count decreased	X	X
	White blood cell decreased	X	X
	Anemia	X	X
General disorders and administration site conditions	Fatigue	X	X
	Injection site reaction		X
Gastrointestinal Disorders	Nausea	X	X
	Vomiting	X	X
	Diarrhea		X
	Constipation		X
	Number of stools	X	
Renal and urinary disorders	Chronic kidney disease (decreased creatinine clearance)	X	X
Skin and subcutaneous tissue disorders	Rash, maculopapular	X	X
Nervous system disorders	Peripheral sensory neuropathy	X	X
Constitutional Symptoms	Insomnia	X	X
Vascular Disorders	Thromboembolic event	X	X

10.61 Submit via appropriate MCCC Case Report Forms (i.e., paper or electronic, as applicable) the following AEs experienced by a patient and not specified in Section 10.6 (above):

10.611 Grade 2 AEs deemed *possibly, probably, or definitely* related to the study treatment or procedure.

10.612 Grade 3 and 4 AEs regardless of attribution to the study treatment or procedure.

10.613 Grade 5 AEs (Deaths)

10.6131 Any death within 30 days of the patient's last study treatment or procedure regardless of attribution to the study treatment or procedure.

- 10.6132 Any death more than 30 days after the patient's last study treatment or procedure that is felt to be at least possibly treatment related must also be submitted as a Grade 5 AE, with a CTCAE type and attribution assigned.
- 10.62 Refer to the instructions in the Forms Packet (or electronic data entry screens, as applicable) regarding the submission of late occurring AEs following completion of the Active Monitoring Phase (i.e., compliance with Test Schedule in [Section 4.0](#)).
- 10.7 All serious adverse events (SAEs) will be followed until resolution or death.

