The primary goal of this trial is to compare the time to progression of the standard treatment arm (Arm A) to the experimental arm (Arm B). We will conduct a randomized trial comparing the experimental arm against the standard treatment arm. We will enter 45 evaluable patients to each arm of the study using a 1:1 randomization scheme (Pocock et al, 1975). The stratification factors that will be used are listed in Section 5.0. The primary analysis will be a comparison of Arm A to Arm B using a one-sided log-rank test between the two Kaplan-Meier curves. This final analysis will take place after an approximate 24-month accrual period and after 52 total progressions have occurred or the last patient has been followed for at least 2 years (whichever occurs first). Additionally, we assume a constant accrual rate over the course of the study and that we will not have a significant lost to follow-up issue, as historically lost to follow-up rates in Mayo clinic trials have been $< 1\%$. A sample size of 45 evaluable patients per arm (90 total) provides 80% power to detect an improvement in median time to progression from 20 months to 40 months (a hazard ratio of 2.0), using a 1-sided log-rank test at a significance level of 0.05. A final decision regarding the level

of promise for the experimental regimen will take all factors into account including TTP, response rate, OS, adverse events, and other relevant factors. All patients meeting the eligibility criteria who have signed a consent form and have begun treatment will be evaluable for the primary endpoint.

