16.34 Adverse Events

All eligible patients that have initiated treatment will be considered evaluable for assessing adverse event rate(s). The maximum grade for each type of adverse event will be recorded for each patient, and frequency tables will be reviewed to determine patterns. Additionally, the relationship of the adverse event(s) to the study treatment will be taken into consideration.

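### Section 16.34 tabulates each patient's maximum adverse event grade without using the required baseline grades, so all-cause lower-grade rates can include unchanged entry conditions

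*Combined protocol and SAP*

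**What the plan says.** Section 16.34 gives the phase II adverse event analysis: "The maximum grade for each type of adverse event will be recorded for each patient", summarized in frequency tables for all eligible patients who started treatment. The one qualifier is that "the relationship of the adverse event(s) to the study treatment will be taken into consideration". Baseline grade, change from baseline and treatment-emergent status are not mentioned.

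The baseline data are required elsewhere. Section 10.6 introduces its table with "Adverse events to be graded at each evaluation and pretreatment symptoms/conditions to be evaluated at baseline per the CTCAE v4.0 grading". Section 6.35 makes the baseline grading a condition of registration, and section 18.11 lists a separate baseline adverse event form.

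Sections 10.611 and 10.612 limit routine reporting to related grade 2 events and to grade 3 and 4 events of any cause. They apply only to events that Table 10.6 does not list. Listed events are graded at every evaluation whatever their grade or cause.

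On use of the results, section 16.31 says that the closing judgement of promise "for the experimental regimen will take all factors into account including TTP, response rate, OS, adverse events, and other relevant factors". Objective 2.22 compares toxicity between the arms.

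**The concern.** A patient who enters with a graded condition will have it graded again on study. If it stays at its entry grade, the maximum-grade rule still records it as that patient's value for the event. In an all-cause table cut at or below that grade, the patient looks the same as one in whom the event began on treatment.

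Entry criteria allow this. Section 3.12 requires only "Creatinine clearance ≥ 30 mL/min" and hemoglobin of at least 8.0 g/dL, and section 3.13 adds "Note: Patients with lytic disease and anemia are eligible".

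At stake is the all-cause, lower-grade part of the safety profile that section 16.31 feeds into the decision on promise. Absolute rates would overstate what happened on treatment, and the ratio of the arms' rates would sit closer to 1 than the ratio for new or worsened events.

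**Working it through.** The plan states no figure on this point, so there is none to reproduce. The check has four steps.

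**1. Which events are exposed.** Table 10.6 has 18 rows. Fourteen are marked at baseline and at each evaluation: creatinine, neutrophils, platelets, lymphocytes, white cells, anemia, fatigue, nausea, vomiting, chronic kidney disease, rash, sensory neuropathy, insomnia and thromboembolism. Three are marked at each evaluation only (injection site reaction, diarrhea, constipation). One is marked at baseline only (number of stools). So 14 + 3 = 17 events are graded on study.

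**2. Which grades are exposed.** Section 3.12 requires ANC of at least 1700 and platelets of at least 100,000. Nobody can enter with grade 4 neutropenia (ANC below 500, section 7.22) or grade 3 or worse thrombocytopenia (below 50,000, section 8.2). Anemia is bounded only by hemoglobin 8.0 g/dL, and the two renal events only by creatinine clearance 30 mL/min. The other nine of the 14 have no entry limit of their own.

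**3. Size of the excess.** Assumptions, none of them from the documents:
- b = share of patients entering with the condition at or above the grade tabulated
- w = share of those who worsen on study
- p = onset rate among patients without it
- b and w are equal in the two arms, and every entry condition is still present at one or more on-study evaluations

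Formulas:
- Raw rate = b + (1-b)p
- Treatment-emergent rate = (1-b)p + bw
- Excess = b(1-w)

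With the planned 45 evaluable patients per arm (section 16.31), the excess is 45 × b(1-w):

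| b | w = 0 | w = 20% | w = 40% |
|---|---|---|---|
| 0 | 0 | 0 | 0 |
| 5% | 2.25 | 1.80 | 1.35 |
| 15% | 6.75 | 5.40 | 4.05 |
| 30% | 13.50 | 10.80 | 8.10 |
| 45% | 20.25 | 16.20 | 12.15 |

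These are upper bounds for each b and w. An entry condition that clears before the first on-study evaluation and does not return drops out of the raw count.

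**4. Effect on the arm contrast.** Take assumed onset rates of 20% and 30%.

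| b | Count | Rates | Ratio | Difference |
|---|---|---|---|---|
| 30% | raw | 44% vs 51% | 1.16 | 7 points |
| 30% | emergent, w = 0 | 14% vs 21% | 1.50 | 7 points |
| 30% | emergent, w = 20% | 20% vs 27% | 1.35 | 7 points |
| 30% | emergent, w = 40% | 26% vs 33% | 1.27 | 7 points |
| 5% | raw | 24% vs 33.5% | 1.40 | 9.5 points |
| 5% | emergent, w = 0 | 19% vs 28.5% | 1.50 | 9.5 points |
| 5% | emergent, w = 20% | 20% vs 29.5% | 1.48 | 9.5 points |
| 5% | emergent, w = 40% | 21% vs 30.5% | 1.45 | 9.5 points |

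The difference over all treated patients is (1-b)(p2 - p1) under both counts, because b and bw cancel between the arms.

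A strict rule of grade above baseline has its own error. If a share r of entry cases resolves and then returns to the entry grade, it misses b × r of patients. At b = 30% that is 0.30 × 0.10 × 45 = 1.35 per arm for r = 10%, and 2.70 for r = 20%.

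**The case against.** **Section 16.34 is silent rather than wrong.** Table 10.6 separates adverse events from pretreatment conditions, and the baseline-only row for number of stools suggests that baseline serves as a reference. A reader might infer that the plan states that unchanged entry conditions are counted. It does not say so, and it does not exclude them either. The point is about what the rule permits when read literally.

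**Attribution already screens.** The five categories in section 10.3 should mark many unchanged conditions as unlikely or unrelated. That stands for related-only tables. It does nothing for all-cause tables. It is also a judgement: section 15.17 lists anemia, fatigue, rash, neuropathy and insomnia as lenalidomide effects, so an unchanged entry condition could still be called possibly related.

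**Objective 2.22 is hardly touched.** A reader might infer that the secondary comparison of toxicity is compromised. The only definition of toxicity, in section 16.232 of the phase I part, means treatment-related events. If it carries over, 2.22 rests on tables that the gap barely reaches. The relevant link is section 16.31, which names adverse events without that restriction.

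**The arms are not distorted against each other.** A reader might infer that the absolute gap between arms shrinks or that one arm is favored. Randomization balances entry conditions on average, and step 4 shows an unchanged expected difference. Section 16.34 plans no test and no risk ratio. This objection stands and limits the gain.

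**The size is assumed.** This also stands. No prevalence, worsening share or onset rate is in the documents.

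**Conclusion.** The concern holds in a limited form. The maximum-grade rule leaves out baseline grades that the protocol requires. Read literally, it lets unchanged entry conditions into all-cause rates at or below the entry grade for 14 events. Absolute rates then rise in both arms by at most b(1-w), and relative contrasts move toward 1. The illustrations assume equal b and w in the arms and persistence of the entry grade; at b = 0 there is no effect.

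The expected risk difference, related-only tables and the primary endpoint are little or not affected. The same holds for the stopping rule in section 16.362, which uses related grade 4 or higher non-hematologic events. Entry limits rule out pre-existing grade 4 neutropenia and grade 3 or worse thrombocytopenia. This is a cheap improvement to the safety tables behind the section 16.31 decision, and it matters only if phase II proceeds.

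**What to change.** In section 16.34, for the 14 events with a baseline grade in Table 10.6, also tabulate by arm the maximum grade among on-study grades above baseline. Count a return to the entry grade only where an intervening evaluation recorded a lower grade. Use all eligible treated patients as the denominator. Add a baseline-to-worst shift table for the laboratory events. Keep the raw maximum-grade and attribution tables, and count injection site reaction, diarrhea and constipation as recorded.

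The cost is SAP wording, one derived variable and one shift table from grades already collected, with no new patients or visits. The recurrence clause needs grades read in visit order. It may miss events that resolve and return between scheduled evaluations: under section 4.0, chemistry is drawn at the end of cycles 1 to 3 and then every third cycle.

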16.35 Over Accrual

If more than the target number of patients are accrued, the additional patients will not be used to evaluate the stopping rule or used in any decision making processes; however, they will be included in final point estimates and confidence intervals.

16.36 Data & Safety Monitoring:

16.361 The principal investigator(s) and the study statistician will review the study at least twice a year to identify accrual, adverse event, and any endpoint problems that might be developing. The Mayo Clinic Cancer Center (MCCC) Data Safety Monitoring Board (DSMB) is responsible

for reviewing accrual and safety data for this trial at least twice a year, based on reports provided by the MCCC Statistical Office.

- 16.362 Adverse Event Stopping Rules (These rules apply to Arm A and Arm B independently for patients in the randomized phase II portion of the study): The stopping rules specified below are based on the knowledge available at study development. We note that the Adverse Event Stopping Rule may be adjusted in the event of either (1) the study re-opening to accrual or (2) at any time during the conduct of the trial and in consideration of newly acquired information regarding the adverse event profile of the treatment(s) under investigation. The study team may choose to suspend accrual because of unexpected adverse event profiles that have not crossed the specified rule below.

Accrual will be temporarily suspended to both arms if at any time we observe events considered at least possibly related to study treatment (i.e. an adverse event with attribute specified as “possible”, “probable”, or “definite”) that satisfy either of the following:

- if 3 or more patients in the first 12 treated patients experience a grade 4 or higher non-hematologic adverse event at least possibly related to treatment.
- if after the first 12 patients have been treated, 25% of all patients experience a grade 4 or higher non-hematologic adverse event at least possibly related to treatment

We note that we will review Grade 4 and 5 adverse events deemed “unrelated” or “unlikely to be related”, to verify their attribution and to monitor the emergence of a previously unrecognized treatment-related adverse event.

16.4 Results Reporting on ClinicalTrials.gov

At study activation, this study will have been registered within the “ClinicalTrials.gov” website. The Primary and Secondary Endpoints along with other required information for this study will be reported on ClinicalTrials.gov. For purposes of timing of the Results Reporting, the initial estimated completion date for the Primary Endpoint of this study is 5.5 years after the study opens to accrual. The definition of “Primary Endpoint Completion Date” (PECD) for this study is at the time the last patient registered has been followed for at least 2 years.

16.5 Inclusion of Women and Minorities

- 16.51 This study will be available to all eligible patients, regardless of race, gender, or ethnic origin.
- 16.52 There is no information currently available regarding differential effects of this regimen in subsets defined by race, gender, or ethnicity, and there is no reason to expect such differences to exist. Therefore, although the planned analysis will, as always, look for differences in treatment effect based on racial and gender groupings, the sample size is not increased in order to provide additional power for subset analyses.
- 16.53 The geographical region served by MCCC has a population which includes approximately 5% minorities. Based on prior MCCC studies involving similar disease sites, we expect about 5% of patients will be classified as minorities by

race and about 45% of patients will be women. Expected sizes of racial by gender subsets are shown in the following table:

Accrual Estimates by Gender/Ethnicity/Race for All Phase 2 and 3 Studies

Ethnic Category	Sex/Gender			
	Females	Males	Unknown	Total
Hispanic or Latino	1	1	0	2
Not Hispanic or Latino	53	65	0	118
Unknown	0	0	0	0
Ethnic Category: Total of all subjects	54	66	0	120
Racial Category				
American Indian or Alaskan Native	0	0	0	0
Asian	0	0	0	0
Black or African American	2	2	0	4
Native Hawaiian or other Pacific Islander	0	0	0	0
White	52	64	0	116
More than one race	0	0	0	0
Unknown	0	0	0	0
Racial Category: Total of all subjects	54	66	0	120

Ethnic Categories: **Hispanic or Latino** – a person of Cuban, Mexican, Puerto Rico, South or Central American, or other Spanish culture or origin, regardless of race. The term “Spanish origin” can also be used in addition to “Hispanic or Latino.”

Not Hispanic or Latino

Racial Categories: **American Indian or Alaskan Native** – a person having origins in any of the original peoples of North, Central, or South America, and who maintains tribal affiliations or community attachment.

Asian – a person having origins in any of the original peoples of the Far East, Southeast Asia, or the Indian subcontinent including, for example, Cambodia, China, India, Japan, Korea, Malaysia, Pakistan, the Philippine Islands, Thailand, and Vietnam. (Note: Individuals from the Philippine Islands have been recorded as Pacific Islanders in previous data collection strategies.)

Black or African American – a person having origins in any of the black racial groups of Africa. Terms such as “Haitian” or “Negro” can be used in addition to “Black or African American.”

Native Hawaiian or other Pacific Islander – a person having origins in any of the original peoples of Hawaii, Guam, Samoa, or other Pacific Islands.

White – a person having origins in any of the original peoples of Europe, the Middle East, or North Africa.

17.0 Pathology Considerations/Tissue Biospecimens: None

18.0 Records and Data Collection Procedures

NOTE (Phase I Only): As of Addendum 5, Anakinra will no longer be provided and all patients will go off study treatment. Event monitoring will no longer be required. Patients may obtain Anakinra commercially and be treated off study.

18.1 Submission Timetables

18.11 Initial Material(s)

Case Report Form (CRF)	Active-Monitoring Phase (Compliance with Test Schedule Section 4.0)
On-Study	≤14 days after registration
Adverse Event - Baseline	
Measurement – Baseline	
SPEP, UPEP, FLC, Immunofixation, FISH, Cytogenetics, PCLI reports	
Bone marrow biopsy report	
Skeletal survey report	
End of Active Treatment/Cancel Notification	Submit ≤14 days after registration if withdrawal/refusal occurs prior to beginning protocol therapy

